Storage, dispensing and return

The AGE reader SU will be stored securely, in a locked room, or locked cupboard or cabinet. Access to the medical device will be limited to the study staff and investigators.

Placebo

No placebo products will be used in the present project.

Known Side Effects

The AGE-Reader has been extensively tested in thousands of adults for several years without any adverse effects. The AGE Reader has CE approval (2085393CE01) to be used as a medical device and thus has passed the rigid safety standard. The amount of ultraviolet light exposure is actually far below the safety limits.

Reference source:

AGE reader. Cardiovascular risk assessment. <http://www.diagnoptics.com/age-reader/>
[Accessed on 12th May, 2016]

TRIAL / STUDY DESIGN

TRIAL / STUDY CONFIGURATION

Studies 1 and 2 will be single-centre.

Study 1: longitudinal/prospective.

Study 2: observational non-randomized proof of principle study where malnourished dialysis participants will receive a dietitian supervised intensive nutritional support.

Primary endpoints

Study 1:

1. Changes in SAF levels after 12 months of follow-up.
2. One-year survival.

Study 2: changes in SAF levels after 6 months of a dietetic intervention (i.e. intensive nutritional support).

Secondary endpoints

Study 1:

- Factors associated with the accumulation of AGE.
- Association of SAF levels with morbidity, biochemical variables (haemoglobin, haemoglobin A1C (HbA1C), urea, creatinine, potassium, phosphate, calcium, sodium, albumin, total proteins, cholesterol, triglycerides, and intact parathyroid hormone), visual function, circulating AGE levels (carboxymethyl lysine [CML] and pentosidine), inflammatory biomarkers (tumour necrosis factor- α [TNF- α], interleukin 6 [IL-6], C reactive protein [CRP] and others) health-related quality of life and nutritional status (energy, protein and fat intake, dietary AGE intake, anthropometry and subjective global assessment [SGA]).

Study 2:

- Association of SAF levels with morbidity, biochemical variables (haemoglobin, HbA1C, urea, creatinine, potassium, phosphate, calcium, sodium, albumin, total proteins, cholesterol, triglycerides, and intact parathyroid hormone), visual function, circulating AGE levels (CML and pentosidine), inflammatory biomarkers (TNF- α , IL-6, CRP and others) health-related quality of life and nutritional status (energy, protein and fat intake, dietary AGE intake, anthropometry and SGA).

Safety endpoints

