- Does not wish to participate.
- Renal transplant.
- Pregnancy or breast feeding or intending pregnancy.
- Expected survival less than one year (for Study 1).

Expected duration of participant participation

Participants will be participating in the Study 1 for five years and in the Study 2 for 24 months.

Removal of participants from therapy or assessments/Participant Withdrawal

Participants will be withdrawn from the study if they withdraw their consent at any point, receive a renal transplant or decline to comply with the dietetic intervention (Study 2). Female participants will be withdrawn from the study if they become pregnant.

Participants may be withdrawn from the study either at their own request or at the discretion of the Investigator. The participants will be made aware that this will not affect their future care. Participants will be made aware (via the information sheet and consent form) that should they withdraw the data collected to date cannot be erased and, with their consent, may still be used in the final analysis.

If participants fail to attend for their study visits, a member of the research team will try to contact them by telephone within 24 hours of their appointment and by written correspondence within a week of the missed appointment. Multiple attempts at contact will be made by the research team over a period of a month before stating that a participant has been lost to follow-up.

With participant consent, data that is collected prior to withdrawal will be kept and analysed as part of the data set. The date, time and reason for participant withdrawal will be documented on the case report form (CRF).

To ensure attainment of adequate numbers of participants for the analysis to be valid, the research team will attempt to recruit other participants to replace any who withdraw from the study.

Informed consent

The process for obtaining participant informed consent will be in accordance with the Research Ethics Committee (REC) guidance, Good Clinical Practice (GCP) and any other regulatory requirements that might be introduced.

The research team have both training and experience in assessing participant capacity and gaining informed consent in the clinical context.

Detailed information will be provided on the study to ensure that participants understand the purpose and potential risks involved. The study will not involve participants who are unable to represent their own interests or are particularly susceptible to coercion.

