Once participants have given their informed consent, relevant participant characteristics will be extracted from electronic data captured in medical records and from a self-report questionnaire at baseline and will include demographic characteristics, educational level, occupation status, family history, duration of renal replacement therapy, dialysis adequacy, aetiology of CKD, medical history (e.g. history of cardiovascular disease, diabetes and hypertension), current co-morbidities, alcohol history, smoking status and current medication. For the PD participants, information regarding the type of PD and the volume of the different PD solutions will also be recorded.

The accumulation of AGE will be assessed by measuring SAF using a validated Autofluorescence Reader (AGE Reader, DiagnOptics, Groningen, The Netherlands) at baseline, 3, 6, 9 and 12 months of follow-up. The method has been previously described by Meerwaldt et al. (2005). As described in the study by Siriopol et al. (2015), "the autofluorescence reader illuminates a skin surface of 1 cm², guarded against surrounding light, with an excitation light source between 300 and 420 nm (peak excitation ≈370 nm). Light from the skin is measured with a spectrometer (AVS-USB2000, Avantes Inc., Eerbeek, The Netherlands) in the 300-600 nm range, using a 200-µm glass fibre". SAF will be measured as the ratio between emission and excitation, calculated in arbitrary units (AU), by

Page 16 of 30

Skin autofluorescence as a risk marker in people receiving dialysis
Protocol draft 4.5 Final Version 2.0 04.10.2017

This protocol is confidential and the property of the University of Nottingham. No part of it may be transmitted, reproduced, published, or used by others persons without prior written authorisation from the University of Nottingham

dividing the intensity of the fluorescent light coming from the skin (measured as area under the curve [AUC] of fluorescent wave lengths between 420 and 600 nm) by the intensity of the emitted light (measured as AUC of wave lengths between 300 and 420 nm) multiplied by 100. For each participant, three measurements will be performed on the volar surface of the lower arm at \approx 10 cm below the elbow, ensuring that the area has normal skin without visible vessels, scars or other abnormalities. For HD participants, only the non-fistula arm will be used and readings will be undertaken within the first hour of HD treatment (Siriopol et al., 2015).

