To compare baseline versus final evaluations, Wilcoxon test or paired t-test will be used in the case of dimensional variables, and McNemar test in the case of categorical variables. Intergroups comparisons will be performed using Mann Whitney test or Student t test for continuous variables and χ^2 test or Fisher's exact test for categorical variables. To determine the significance and strength of associations, Pearson's correlation coefficient will be used for analyses of associations between continuous variables and Spearman rank for nonparametric variables. Linear regression analysis will be used to identify determinants of AGE accumulation. Cox proportional hazards models will be used to investigate the prognostic value of the accumulation of AGE for predicting mortality. A p-value less than or equal to 0.05 will be considered to have statistical significance.

Sample size calculation of Study 1 was performed by using the software nQuery Advisor v.6.0.

Sample size Study 1:

The primary outcome for sample size determination is one-year survival in relation to increased SAF levels in people on HD and PD. With a power of 80%, a two-sided alpha of 5% and an expected hazard ratio of 3.5 and 2.0 in people on PD and HD, respectively (based on similar findings of the studies of Kimura et al. [2014] and Siriopol et al. [2015]), 100 HD and 40 PD participants will be needed.

Sample size Study 2

Since this is a proof of principle study, it would be reasonable to include 40 dialysis participants (either HD or PD).

Assessment of efficacy

Primary endpoints

Study 1:

- Mean change in SAF levels (AU) from baseline to 12 months of follow-up.
- One-year survival.

Study 2:

Mean change in SAF levels (AU) after 6 months of a dietitian supervised intensive nutritional support intervention

Secondary endpoints

Study 1:

- Regression coefficients for identifying factors associated with the accumulation of AGE.
- Correlation coefficients for analysing the association of SAF levels with morbidity, biochemistry, circulating AGE levels, inflammatory biomarkers, visual function, health-related quality of life and nutritional status.

Study 2:

- Changes in biochemistry, circulating AGE levels, inflammatory biomarkers, visual function, health-related quality of life and nutritional status.

Assessment of safety

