Tolerability and safety of the nutritional support intervention during the proof of principle study (Study 2) will be assessed by direct interview. If any serious adverse event (SAE) is reported during the study, it will be recorded on an appropriate SAE report form.

Procedures for missing, unused and spurious data

All SAF measurements, biochemistry, nutritional and quality of life assessments for Study 1 and 2 will be used in the statistical analysis, including data from participants who did not complete the entire study protocol.

Definition of populations analysed

Study 1:

Full Analysis set: All participants included in the protocol for whom at least one post-baseline assessment of the primary endpoint is available.

Per protocol set: All participants in the Full Analysis set who are deemed to have no major protocol violations that could interfere with the objectives of the study.

Study 2:

Full Analysis set: All randomised participants, who participated in at least one treatment and for whom at least one post-baseline assessment of the primary endpoint is available.

Per protocol set: All participants in the Full Analysis set who are deemed to have no major protocol violations that could interfere with the objectives of the study.

ADVERSE EVENTS

The occurrence of an adverse event as a result of participation within this study is not expected and as such no adverse event data will be collected.

ETHICAL AND REGULATORY ASPECTS

ETHICS COMMITTEE AND REGULATORY APPROVALS

The study will not be initiated before the protocol, informed consent forms and participant information sheets have received approval / favourable opinion from the REC, and the respective NHS Research & Development (R&D) department. Should a protocol amendment be made that requires REC approval, the changes in the protocol will not be instituted until the amendment and revised informed consent forms and participant information sheets (if appropriate) have been reviewed and received approval / favourable opinion from the REC and R&D departments. A protocol amendment intended to eliminate an apparent immediate hazard to participants may be implemented immediately providing that the REC are notified as soon as possible and an approval is requested. Minor protocol amendments only for logistical or administrative changes may be implemented immediately; and the REC will be informed.

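### The only test named for Study 1's 12-month SAF change compares two time points; if the second is month 12, it cannot use interim readings or non-completers as the plan promises

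*Combined protocol and SAP*

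**What the plan says.** All references are to the combined protocol and SAP.

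- **Endpoint.** Trial/Study Configuration lists "Changes in SAF levels after 12 months of follow-up" as the first Study 1 primary endpoint. Assessment of Efficacy restates it as "Mean change in SAF levels (AU) from baseline to 12 months of follow-up".
- **Test.** Statistics, Methods: "To compare baseline versus final evaluations, Wilcoxon test or paired t-test will be used in the case of dimensional variables". The synopsis names the same tests. Linear regression is assigned to determinants of AGE accumulation, Cox models to mortality, and the Mann-Whitney or Student t-test to comparisons between groups.
- **Schedule.** In Study 1, SAF is read "at baseline, 3, 6, 9 and 12 months of follow-up", then yearly for up to five years.
- **Data to be used.** Under the procedures for missing data, all SAF measurements "will be used in the statistical analysis, including data from participants who did not complete the entire study protocol".
- **Full Analysis set, Study 1.** "All participants included in the protocol for whom at least one post-baseline assessment of the primary endpoint is available".
- **Loss.** "Participants will be withdrawn from the study if they withdraw their consent at any point, receive a renal transplant". The Compliance section also counts an uncompleted study day as a withdrawal. As for replacement, "the research team will attempt to recruit other participants to replace any who withdraw from the study".

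**The concern.** A paired test needs both members of the pair. With month 12 as the second member, a participant read at months 0, 3, 6 and 9 contributes nothing to the primary estimate, although the missing-data section promises to use those readings. The Full Analysis set also appears to admit that person. No repeated-measures model, imputation or carry-forward rule fills the gap.

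Whether SAF rises over time is the first primary objective. People who leave before month 12 may differ in SAF change from those who stay, and the paired mean then describes the stayers only. Replacing withdrawals restores the number of participants, but the replacements are subject to the same selection.

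**Working it through.** **1. Readings used (planned numbers).** 100 HD + 40 PD + up to 30 incident = 170 participants. Scheduled first-year readings: 170 × 5 = 850. A baseline to month-12 paired test uses at most 170 × 2 = 340. The other 170 × 3 = 510 (60%) do not enter the change test. They may still enter the correlations or regressions.

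**2. Participants used (loss rate assumed, since none is given).** If a share d lacks month 12, the test uses 170(1 − d) people, and its standard error grows by √(1/(1 − d)) relative to no loss.

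| d | analysed | SE factor |
|---|---|---|
| 10% | 153 | 1.05 |
| 20% | 136 | 1.12 |
| 30% | 119 | 1.20 |

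**3. Loss unrelated to SAF.** There is no bias. In a simulation with N = 170, true rise 0.20, slope SD 0.35, between-person SD 0.8 and error SD 0.25 (all assumed), with 73–89% completing, both the paired mean and a repeated-measures model with visit as a category gave 0.20. Their standard errors were 0.041–0.045 and 0.039–0.041. With complete data and unstructured covariance, the categorical model's change is the paired mean, so nothing is gained.

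**4. Loss among the living related to the SAF change already observed.** Assumed: rise 0.20 AU/year, baseline SD 0.9, slope SD 0.3–0.6, error SD 0.2, no deaths, logistic loss after months 3, 6 and 9.

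| Lacking month 12 | Completer mean, odds of loss × 1.5–2 per SD of rise | Completer mean, reverse direction |
|---|---|---|
| 10% (17 of 170) | 0.165–0.188 | 0.211–0.237 |
| 20% (34 of 170) | 0.128–0.177 | 0.224–0.273 |
| 25% (about 43 of 170) | 0.112–0.172 | 0.227–0.288 |

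At 20% loss the categorical-visit model returns 0.20. With n = 100, 20% loss and odds doubled or halved, the paired 95% interval covers 0.20 in 84–88% of trials. Replacing each loss once moved the completer mean by no more than 0.003.

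**5. Loss related to a person's unobserved slope.** No model on these data fully repairs this. A likelihood model with linear time gave 0.156–0.245, against 0.094–0.306 for completers.

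**6. Death as the only loss.** The completer mean matched the true mean of 12-month survivors within 0.001. Any gap from the whole enrolled cohort is then a choice of target.

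**7. Why visit should be a category.** Suppose mean SAF rises 0.20 by month 3 and stays there. With complete data, the fitted linear slope over t = 0, 0.25, 0.5, 0.75, 1 is Σ(t − 0.5)y / Σ(t − 0.5)². The numerator is −0.05 + 0 + 0.05 + 0.10 = 0.10 and the denominator is 0.625, so the model reports 0.10/0.625 = 0.16 for a true 12-month change of 0.20. A rise only after month 9 also gives 0.5 × 0.20/0.625 = 0.16. With early rise, plateau and 20% loss, the linear model gave 0.18–0.19 even when loss was random.

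**The case against.** **The plan does not say that it excludes anyone.** A reader might infer that it drops Full Analysis set members who lack month 12. That needs two readings the text does not fix: that the final evaluation is month 12, and that an assessment of the primary endpoint means any SAF reading. If the final evaluation is the last available reading, or if only a month-12 value counts as an assessment, nobody in the set is dropped. This stands, and it limits the claim. But a last-reading test would mix 3-month and 12-month changes under an endpoint fixed at 12 months. The narrow reading of the set would still leave non-completers' data out of the mean change.

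**Nothing shows that the SAF result will be biased.** A reader might infer this too. No section links transplant, withdrawal or missed visits to SAF change. The link the plan does expect is from SAF to death, where the completer mean is right for survivors. This also stands.

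**Loss may be small.** Study 1 excludes people expected to survive less than a year. HD participants attend at least three times a week, a reading takes under five minutes, and missed visits trigger contact attempts for a month. The 20–25% rows above are therefore assumptions, and the lowest and highest means need slope SD 0.6, three times the assumed rise. At slope SD 0.3, with 10–20% loss and odds × 1.5–2, the paired test still detects the rise in 94–99% of trials at n = 100; at 0.6 it does so in 45–73%.

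**A model changes the target.** Its mean extrapolates past death and transplant, although survival is co-primary. That is a reason to state both targets and keep the paired analysis.

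**Conclusion.** The concern holds in a limited form. For the Study 1 mean SAF change, the Methods section names only a two-point paired test, and no stated method delivers what the missing-data section promises for non-completers and interim readings. This rests on taking the final evaluation to be month 12. It concerns the change test only, because interim readings may serve secondary analyses.

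The consequence depends on why people are lost. If loss is unrelated to SAF, the cost is modest precision. If loss among the living follows observed SAF change, the bias can go either way: at 20% loss, about 0.13–0.18 or 0.22–0.27 against a true 0.20. Every input to those figures is assumed, and the actual size is unknown. The change is worth making because it affects a primary objective and uses readings already scheduled.

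**What to change.** 1. Define the final evaluation as month 12 for the Study 1 primary SAF endpoint.
2. Estimate the 12-month change with a likelihood-based repeated-measures mixed model on all readings at 0, 3, 6, 9 and 12 months. Include visit as a category, cohort (prevalent HD, prevalent PD, incident) and cohort-by-visit. Report the month-12 change per cohort with a 95% confidence interval.
3. Use a linear random-slope model as a secondary analysis only.
4. Keep the paired test as the completer/survivor analysis. State the target of each analysis, including that the model's mean extrapolates past death and transplant.
5. Report how many lack a month-12 reading, by reason: death, transplant, other withdrawal.

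**Cost.** SAP wording and slightly more analysis; no new data, and the named software can fit such models. The model assumes that loss depends only on observed readings, and it gives no precision gain over the paired test when data are complete. Recruitment began in June 2016, this protocol version is dated October 2017, and the background section reports that baseline data have been analysed. The sponsor should therefore document that the change was made without reference to follow-up SAF results.

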| Description of interventions | 
Study 1: no intervention.
 
Study 2: Dietitian supervised nutritional support aimed at improving malnutrition in addition to standard dietetic advice consistent with United Kingdom Renal Association guidelines (Wright and Jones, 2010).
 |
| Duration of study | 
Study 1: Participant recruitment will begin on June 2016 with an anticipated recruitment period of 14 months. Therefore, all baseline data and measurements will be collected and performed between June 2016 and August 2017.
 
Participant Duration: once recruited, all participants will be followed-up for up to five years; consequently, it is expected that the study will be completed by August 2022.
 
Study 2: Participant recruitment will begin in December 2017 with an anticipated recruitment period of 6 months. Therefore, all baseline data and measurements will be collected and performed between December 2017 and June 2018.
 
Participant Duration: once recruited, all participants will be followed-up for 24 months; consequently, it is expected that the study will be completed by June 2020.
 |
| Randomization and blinding | Studies 1 and 2: no randomization required. |
| Outcome measures | 
Study 1:
 
 • Primary outcomes: 
 1. Changes in SAF levels over 1 year. 2. One-year survival. • Secondary outcomes: factors associated with the accumulation of AGE, morbidity, biochemistry, visual function, quality of life and nutritional status. 
Study 2:
 
 • Primary outcomes: changes in SAF levels. • Secondary outcomes: biochemistry, visual function, quality of life and nutritional status. |
| Statistical methods | Intragroup comparisons will be performed using Wilcoxon test or paired t-test for dimensional variables and McNemar test for categorical variables. Intergroup comparisons will be performed using Mann Whitney test or Student t test for continuous variables and χ^2 test or Fisher's exact test for categorical variables. To determine the significance and strength of associations, Pearson's correlation coefficient will be used for continuous variables and Spearman rank for nonparametric variables. Linear |

| | |
|--|--|

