
All participants will provide written informed consent. The Informed Consent Form will be signed and dated by the participant before they enter the study. The Investigator will explain the details of the study and provide a Participant Information Sheet, ensuring that the participant has sufficient time to consider participating or not. The Investigator will answer any questions that the participant has concerning study participation.

The decision regarding participation in the study is entirely voluntary. The Investigator or their nominee shall emphasize to them that consent regarding study participation may be withdrawn at any time without penalty or affecting the quality or quantity of their future medical care.

Informed consent will be obtained from each participant before they undergo any interventions (including physical examination and history taking) related to the study. One copy of this will be kept by the participant, one will be kept by the Investigator, and a third will be retained in the participant's hospital records.

Should there be any subsequent substantial amendment to the final protocol, which might affect a participant's participation in the study, continuing consent will be obtained using an amended Consent Form which will be signed by the participant.

TRIAL / STUDY TREATMENT AND REGIMEN

Study 1 - longitudinal/prospective study

100 participants undergoing maintenance HD treatment (dialysis vintage greater than 3 months), 40 PD participants with a dialysis vintage greater than 3 months and up to 30 incident participants starting either HD or PD treatment (dialysis vintage less than 3 months) will be recruited from the Renal Unit of the Department of Nephrology at the Royal Derby Hospital and will be followed-up for five years.

Data collection and study procedures/assessments

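### The t-test named for between-group comparisons assumes equal variances, so in the unequal Study 1 cohorts its 5% level is not assured; Welch's test would hold it at little cost

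*Combined protocol and SAP*

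**What the plan says.** The Methods part of the STATISTICS section states: "Intergroups comparisons will be performed using Mann Whitney test or Student t test for continuous variables". The synopsis, under Statistical methods, repeats it: "Intergroup comparisons will be performed using Mann Whitney test or Student t test for continuous variables". The threshold is: "A p-value less than or equal to 0.05 will be considered to have statistical significance". Neither place says how the choice between the two tests is made, which groups are compared, or what happens if the variances differ.

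The section on study treatment and regimen sets three Study 1 cohorts of unequal size. The prevalent cohorts number 100 on HD and 40 on PD; the third is described as "up to 30 incident participants starting either HD or PD treatment". No SD is given for SAF or any other variable.

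The two Study 1 primary endpoints have other methods in the same Methods paragraph. Baseline-to-final change is tested by a paired t-test or Wilcoxon test, and mortality by Cox models.

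**The concern.** Student's two-sample t-test uses one pooled variance. Its reference distribution is therefore right only if both groups have the same variance as well as the same mean. With equal group sizes a breach matters little. With sizes such as 100 and 40 it matters, and its direction depends on which group is more variable. If the smaller group has the larger SD, the pooled estimate understates the standard error and the test rejects too often. If the larger group has the larger SD, the test rejects too rarely and loses power.

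At stake is a comparison of, for example, mean SAF or mean SAF change between HD and PD, or between prevalent and incident participants. A difference in spread could be reported as a difference in means, or a real difference missed, and the stated threshold would not show it.

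**Working it through.** **Inputs from the documents.** Cohorts of 100, 40 and (at most) 30; threshold 0.05, taken as two-sided.

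**Assumptions.** Normal data, equal means, and r = SD of the smaller group divided by SD of the larger. The documents give no value for r, so a range is shown.

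**Formula.** Set the larger group's SD to 1, with sizes n1 (larger) and n2 (smaller).

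- True variance of the mean difference: V = 1/n1 + r²/n2
- Expected pooled variance: S² = [(n1 − 1) + (n2 − 1)r²] / (n1 + n2 − 2)
- Variance that Student uses: P = S²(1/n1 + 1/n2)
- θ = √(V/P), and the large-sample rejection rate is 2[1 − Φ(1.96/θ)]

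**The plan's own figure.** At r = 1, V = P, so θ = 1 and the rate is 5.0% for every pair. The nominal level is reproduced.

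**Worked cases at r = 1.5**

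- 100 v 40: V = 0.01 + 2.25/40 = 0.06625. S² = (99 + 39 × 2.25)/138 = 1.3533. P = 1.3533 × 0.035 = 0.04736. θ = 1.183, rate 9.7%.
- 100 v 30: V = 0.01 + 2.25/30 = 0.085. S² = (99 + 29 × 2.25)/128 = 1.2832. P = 1.2832 × 0.04333 = 0.05561. θ = 1.236, rate 11.3%.
- 40 v 30: V = 0.025 + 0.075 = 0.1. S² = (39 + 29 × 2.25)/68 = 1.5331. P = 1.5331 × 0.05833 = 0.08943. θ = 1.057, rate 6.4%.

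**Simulation.** Drawing the mean difference and the two variances from their exact sampling distributions (at least 2,000,000 replicates per cell) gives these rejection rates for Student's test:

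| Pair | r = 0.67 | r = 1 | r = 1.25 | r = 1.5 | r = 2 |
|---|---|---|---|---|---|
| 100 v 40 | 2.1% | 5.0% | 7.4% | 9.7% | 13.3% |
| 100 v 30 | 1.6% | 5.0% | 8.2% | 11.2% | 16.2% |
| 40 v 30 | 3.9% | 5.0% | 5.8% | 6.4% | 7.4% |

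For r of 1 and above, formula and simulation agree to about 0.1 point; for example, the formula gives 7.5% for 100 v 40 at r = 1.25 and 16.3% for 100 v 30 at r = 2.

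**Welch's test** in the same simulations rejects in 5.0% of trials (4.97% to 5.03%) in every cell.

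**Mann-Whitney**, the plan's alternative (10,000 replicates per cell), rejects in 7.8% of trials at r = 1.5 and 9.6% at r = 2 for 100 v 40, and in about 8% and 10.5% for 100 v 30.

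**The case against.** The strongest reply is that little depends on this sentence. Neither Study 1 primary analysis is a two-sample t-test, the Study 1 secondary endpoints are expressed as regression and correlation coefficients, and Study 2 has a single group. No objective asks for a difference in means between HD and PD or between incident and prevalent participants. All of this stands, and it limits the point to secondary or descriptive comparisons.

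The second reply is that the spread is unknown. That also stands. The background section reports different correlates of SAF in PD and HD, but this does not show which group is more variable, or by how much. The plan will present SDs where appropriate, so unequal spread may be visible. Seeing it does not correct a p value already computed with a pooled variance.

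A reader might infer more than the documents support:

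- *That every comparison uses Student's test.* The plan offers Mann-Whitney as an alternative.
- *That the error rate is two to three times nominal across the cohorts.* Rates of about that size need one of the pairs with 100 and a smaller group roughly 1.5 to 2 times as variable. They do not arise for 40 v 30, and in the other direction the test is conservative.
- *That survivors will be compared with non-survivors by t-test.* The plan assigns mortality to Cox models and gives no such split.
- *That Mann-Whitney is itself in error.* Rejecting when spreads differ is legitimate under its own null of identical distributions. It simply should not be relied on to give a 5% test of a difference in means.

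**Conclusion.** The point holds as a cheap improvement of minor consequence. Where the t-test is applied to the 100 v 40 or 100 v 30 pairs, the 5% level rests on an equal-variance assumption that the plan does not state. The actual rate could lie anywhere from about 2% to 16% for SD ratios between 0.67 and 2. For 40 v 30 the range is about 4% to 7%.

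This rests on three assumptions: that the recruited cohorts are the groups compared, which is natural but not stated; that the data are roughly normal; and that the SD ratio departs from 1, which the documents cannot settle. The results do not show that any planned comparison will be wrong, and they do not bear on the paired SAF change or the Cox analysis of survival.

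**What to change.** In the synopsis (Statistical methods) and in the Methods part of the STATISTICS section, replace Student's t-test by Welch's t-test (equal variances not assumed) for two-group comparisons of means, and report each difference with its 95% CI. Do not present Mann-Whitney as a way to restore the 5% level for a difference in means. Listing the pairs to be compared would also make the sentence checkable.

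The edit is one phrase in two places, and the planned software can run the test. The statistical cost arises only if variances are in fact equal. For a true difference of 0.5 SD, power falls from 75.6% to 75.1% for 100 v 40 (0.5 point), and from 69.5% to 68.0% (1.5 points) if the two prevalent cohorts are pooled (100 + 40 = 140) and compared with 30 incident participants.
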